## **2.6 Overall Impact**

Our study focuses on patients with cancer, but knowledge gained about safety and immunologic correlates is expected to be applicable to other patients at high risk for COVID-19-related morbidity and mortality as well as to future viral pandemics. Using each patient's baseline nasopharyngeal viral load, we will evaluate to what extent the study regimen reduces viral load relative to supportive care only. Assessment of nasopharyngeal viral load at multiple time points will enable evaluation of early and long-term effects of the study regimen in controlling viral replication. A reduction in nasopharyngeal viral load by PCR may also reflect reduced likelihood of transmission of virus to others. As described in the Statistical Plan (Section 19), the study is non-randomized and each patient will serve as their own control regarding baseline, on-treatment, and post-treatment nasopharyngeal viral load. In addition, comparisons will be made with historical controls in which Roswell Park patients with COVID-19 were treated with standard of care and longitudinal viral load was monitored as standard of care. As described in the demonstration of safety of this regimen and reduction of nasopharyngeal viral load will establish the foundation for a larger randomized trial powered for clinical efficacy, such as reduction in respiratory failure and mortality.

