### **Primary Endpoint**

- The primary safety endpoint is the frequency of grade 3 or 4 AEs considered to be possibly, probably, or definitely related to the treatment regimen.

**Phase IIa.** The Phase IIa component of the trial is designed to be a single arm trial of IFN $\alpha$  (at MTD, if reached, otherwise at 20 MU/M) + rintatolimod along with the best available standard of care. Using each patient's baseline nasopharyngeal viral load, we will evaluate to what extent the study regimen reduces viral load relative historical institutional benchmarks. The sample size will be n=10.

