### 19.2.2 Efficacy

In order to compare the AUC between rintatolimod versus historical institutional benchmarks we will use the highly efficient approach proposed by Chandrasekhar et al (48). Ct values measured at baseline (Day 0), Days 3, 7 and 14 will be used to measure the AUC using a standard trapezoidal rule where the AUC for the  $i$ th subject in group  $k$  ( $k=1$  for rintatolimod and  $k=2$  for control) as  $AUC_{jk} = \sum_{i=1}^m c_j Y_{ijk}$  where  $t_1 = 0, t_2 = 3, t_3 = 7, t_4 = 14, t_5 = 30$ ,  $m = 5$ , the  $Y_{ijk}$ 's denote the corresponding Ct values per subject at the respective time points and

$$c_j = \begin{cases} \frac{t_{j+1} - t_j}{2}, & j = 1 \\ \frac{t_j - t_{j-1}}{2}, & j = m \\ \frac{t_{j+1} - t_{j-1}}{2}, & \text{otherwise} \end{cases}$$

If a Ct value is  $>40$  it will be considered right censored for the purpose of this analysis, which corresponds to a non-detectable level. We can re-express this formulation using a linear mixed model with details given exactly as in Chandrasekhar et al. (48). A large AUC value for a respective subject is a measure of treatment efficacy as compared to a subject with a lower AUC

Roswell Park Protocol No.: I-659920

value. The primary test of efficacy will be H0:  $AUC=130$  (log2 copies) x day versus H1:  $AUC>130$  (log2 copies) x day.

The secondary clinical efficacy endpoints of (i) progression of infection requiring hospitalization in patients who were not inpatients at study entry; (ii) respiratory failure requiring mechanical ventilation; and (iii) death within 30 days will be compared using Fisher's exact test. Time to a Ct value of non-detectable will be examined using an exact discrete time-to-event Cox model. The analysis of correlative endpoints will be primarily descriptive and graphical in nature.

The primary test of efficacy will be one-sided and tested at level alpha=0.05. All additional tests will be two-sided and tested at level alpha=0.05.

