### **19.3 Sample Size Justification**

The sample size was based on preliminary data gathered at Roswell Park on patients and employees. The values were similar between the two study groups. The Ct values collected at baseline for n=20 patients and employees had an average of 24.1 log2 copies with a standard deviation of 6.5. The standard deviations after baseline was approximately 4.5 as the Ct values increased. The preliminary estimate for the AUC based on our pilot data is 130 (log2 copies) x day, which is the basis for our null hypothesis. The between time point correlation was estimated to be approximately rho=0.3. Given n=10 subjects we will be able to detect and increase in the AUC to an average of 144 (log2 copies) x day (efficacy) or greater than our assumed institutional benchmark of 130 (log2 copies) x day at power=0.80 and alpha=0.05(one-sided). We simplified this calculation assuming no censoring, which will be accounted for in the final analysis and assumed a compound symmetry covariance structure with the correlation estimate described above.

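### The primary test compares a Ct AUC that contains the pre-treatment value with a fixed 130 and states no baseline adjustment, so a systematic baseline difference from the pilot biases it

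*Combined protocol and SAP*

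**What the plan says.** Section 19.2.2 defines the primary endpoint as a trapezoid sum of Ct values in which Day 0 is one term. It reads a higher sum as benefit: "A large AUC value for a respective subject is a measure of treatment efficacy as compared to a subject with a lower AUC". The null is a mean of 130 against a larger mean, and "The primary test of efficacy will be one-sided and tested at level alpha=0.05". The only adjustment described is right-censoring of Ct above 40. Details of the mixed model are left to a cited method paper.

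Other sections promise that baseline will be used. Section 2.6 says "each patient will serve as their own control". Section 10 says the effect will be judged using each patient's baseline load. The Phase IIa paragraph of Section 19.1 opens the same way and continues "we will evaluate to what extent the study regimen reduces viral load relative historical institutional benchmarks".

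Section 19.3 supplies the benchmark: "The preliminary estimate for the AUC based on our pilot data is 130 (log2 copies) x day". Baseline Ct in 20 patients and employees "had an average of 24.1 log2 copies with a standard deviation of 6.5". Section 19.4 confirms that the trial is not randomized.

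**The concern.** A patient enrolled later in the infection can have a higher Ct before the first dose, and therefore a larger AUC, with no drug effect. Section 3.1 requires symptomatic, PCR-confirmed infection but sets no limit on symptom duration or baseline Ct. The trial enrols patients with cancer, while the pilot mixed patients and employees. If trial patients start systematically higher or lower than the pilot, that difference enters the primary result with nothing in the stated test to remove it. A systematic excess would look like efficacy, and a systematic deficit would hide it. The own-control language may lead a reader to think this has been dealt with.

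**Working it through.** **Inputs (Section 19.3):** SD 6.5 at baseline and 4.5 afterwards, rho = 0.3 with compound symmetry, n = 10, target +14 over 130, one-sided alpha 0.05. **Weights (Section 19.2.2):** the text lists Days 0, 3, 7 and 14, giving 1.5, 3.5, 5.5, 3.5. The formula adds Day 30, giving 1.5, 3.5, 5.5, 11.5, 8. Both grids are shown.

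**1. The plan's own figure.** Variance of the AUC, Days 0-14:
- baseline term: 1.5² × 6.5² = 95.1
- later visits: 4.5² × [54.75 + 0.3 × (12.5² − 54.75)] = 20.25 × 85.2 = 1725.3
- cross term: 2 × 0.3 × 1.5 × 6.5 × 4.5 × 12.5 = 329.1
- total 2149.4, so SD = 46.4

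Detectable difference = 46.4 × (1.645 + 0.842)/√10 = 36.5 by the normal formula, or 39.5 by the t version. Power for +14 is 0.22 (t). The stated 14 at power 0.80 is not reproduced; it would need an SD of about 17.8. On Days 0-30 the SD is 95.7 and the detectable difference 75.3. That shortfall is a separate matter, but it limits what baseline adjustment can achieve.

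**2. AUC change per 1 Ct of baseline difference.** Slope = 1.5 + 0.3 × (4.5/6.5) × (sum of later weights).
- Days 0-14: 1.5 + 0.2077 × 12.5 = 4.10
- Days 0-30: 1.5 + 0.2077 × 28.5 = 7.42

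**3. Error rate with no drug effect and a systematic +2 Ct difference** (one-sample t, 9 df).
- Days 0-14: shift 8.2, SE 46.4/√10 = 14.7, rejection 0.13
- Days 0-30: shift 14.8, SE 95.7/√10 = 30.3, rejection 0.12

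In the other direction, with a true +14 and a −2 Ct difference on Days 0-14, power falls from 0.22 to 0.10.

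**4. Dependence on persistence (Days 0-14).** If only the Day 0 term moves (1.5 per Ct), the +2 Ct rejection rate is 0.073. If the difference persists unchanged at every visit (14 per Ct), it is 0.55. The 0.13 is what the plan's rho implies.

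**5. Effect of a baseline covariate (Days 0-14).** Residual SD = √(2149.4 − 4.10² × 6.5²) = 38.0, so baseline explains 33% of the AUC variance. Power for +14 rises from 0.22 to 0.29 if the slope is known. In a simulation with the slope estimated from 10 patients, baseline centred on 24.1 and the intercept tested on 8 df, power is about 0.26. Error under a +2 Ct difference returns to 0.05.

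**6. Effect of subtracting baseline × 14 days.** Slope = 4.10 − 14 = −9.9. Variance = 2149.4 + 14² × 42.25 − 2 × 14 × 4.10 × 42.25 = about 5585, so SD = 74.7. Power for +14 falls to 0.14.

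**7. Scale of the benchmark.** A flat Ct of 24.1 already gives 24.1 × 14 = 337 over 14 days and 24.1 × 30 = 723 over 30. Neither grid can give a raw AUC of 130.

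**The case against.** Four objections carry weight.

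- **Chance imbalance.** A reader might infer that ordinary chance differences in baseline make the test invalid. They do not. Chance variation in baseline is part of the AUC variance and so of the test's standard error. One SE of mean baseline Ct (6.5/√10 = 2.06) moves the AUC by 8.4 units. That is a loss of precision at n = 10, not an excess of false positives. Nor does a contrast of 10 trial patients with 20 pilot subjects describe the stated test, which is one-sample against a constant. Section 19.3 gives the 20 for baseline Ct and does not say how many people underlie the 130.
- **The cited paper.** The mixed-model details are deferred to a paper that could not be checked here. The supportable statement is that the plan states no adjustment, not that none will be made.
- **No imbalance is shown.** A reader might infer that the trial population will differ from the pilot. The documents do not establish that. Section 19.3 reports similar values in patients and employees, though this does not show that 10 trial patients will match them.
- **What 130 is.** It might be a baseline-subtracted AUC (130/14 = a mean rise of 9.3 Ct), which would honour the own-control wording. The plan never defines a subtraction, and the reading fits the stated SDs poorly (detectable difference 63.7, not 14). It would not remove the problem either, because the baseline slope would then be −9.9.

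**Conclusion.** The point holds for systematic baseline differences. The plan says baseline will be used, but the primary test as written does not use it. Under the plan's SDs and rho = 0.3, a +2 Ct difference with no drug effect raises the one-sided error from 0.05 to about 0.13 (Days 0-14) or 0.12 (Days 0-30). A difference of the opposite sign costs power. The 2 Ct is an illustrative assumption, since the documents do not say how large a difference to expect. The result also assumes compound symmetry and no censoring, as in Section 19.3, and it varies with persistence from 0.073 to 0.55 on Days 0-14. The comparison of these shifts with the 14-unit target is provisional until the scale of the 130 is settled. Adjustment should not be read as a rescue of the design: power for +14 stays below 0.30 on Days 0-14 even with the slope known.

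**What to change.** 1. First reconcile the time grid (Day 14 or Day 30) and state how the 130 was obtained, on what window and from how many people.
2. Put baseline Ct into the primary model as a covariate. Where patient-level historical data can be obtained (Section 2.6 describes longitudinal monitoring of historical patients), fit both groups together. Otherwise centre baseline on the benchmark mean of 24.1 and test the intercept against the reconciled benchmark. This fallback still treats both the benchmark and 24.1 as exact, so the first option is better.
3. State which pre-dose swab is Day 0, because Section 11.4 schedules one at screening and one on Day 1.
4. Report the unadjusted test as a sensitivity analysis, and do not use change from baseline or baseline-subtracted AUC as the adjustment.

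The cost is one degree of freedom at n = 10, SAP wording, and some work to assemble historical baseline values. Trial patients need no new measurement. The covariate handles differences in starting Ct only; other differences between the trial and historical patients, such as standard of care, remain.

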### 8.2 Secondary Endpoints\*

- Clinical efficacy will be assessed by the frequency of these complications: (i) progression of infection requiring hospitalization; (ii) respiratory failure requiring mechanical ventilation; and (iii) death within 30 days.

Although the data on outcomes in patients with COVID-19 and cancer are limited, based on the Chinese experience, approximately 40% are expected to have the composite endpoint of respiratory failure requiring mechanical ventilation or death (1). We note the limitations of this

Roswell Park Protocol No.: I-659920

estimate regarding small numbers of patients with cancer and heterogeneity in cancer types and co-morbidities, including older age, smoking, and lung disease (41). If present, acute respiratory distress syndrome (ARDS) will be graded by Berlin criteria (42), which include 3 mutually exclusive categories of ARDS based on degree of hypoxemia: mild ( $200 \text{ mm Hg} < \text{PaO}_2/\text{FIO}_2 \leq 300 \text{ mm Hg}$ ), moderate ( $100 \text{ mm Hg} < \text{PaO}_2/\text{FIO}_2 \leq 200 \text{ mm Hg}$ ), and severe ( $\text{PaO}_2/\text{FIO}_2 \leq 100 \text{ mm Hg}$ ). The degree of ARDS is has been validated as a predictor of mortality in patients with respiratory failure. The Berlin criteria require 5cm H2O as the minimum level of PEEP delivered by a ventilator or CPAP for diagnosing ARDS; if PEEP is not administered, then ARDS cannot be diagnosed. In addition, the Berlin criteria require excluding hydrostatic pulmonary edema by clinical judgement or with echocardiograph as a cause of respiratory failure. Although the study is not powered for the clinical endpoint, in case that any of the elements of the clinical efficacy endpoint will reach statistical difference between arms, such clinical endpoint will be considered as an overruling endpoint of efficacy

- Evaluate kinetics of viral load as Ct values in peripheral blood in the course of treatment and Days 7 and 14 (40).
- Determine the kinetics of changes of the immune subsets and circulating inflammatory mediators (including CRP, cytokines, chemokines, interferons) in peripheral blood in the course of treatment. Plasma and PBMCs will be cryopreserved for future exploratory studies, including the assessment of intracellular signaling and TCR and BCR repertoires as correlates of response to the study regimen.

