### **Secondary Endpoints**

- Clinical efficacy will be assessed by the frequency of these complications: (i) progression of infection requiring hospitalization; (ii) respiratory failure requiring mechanical ventilation; (iii) death within 30 days and (iv) Time to a Ct value of non-detectable.

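### Ventilation is tested alone and can overrule as the efficacy endpoint, with no rule for death before ventilation, although the only clinical benchmark is ventilation or death combined

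*Combined protocol and SAP*

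**What the plan says.** - **Endpoints.** Sections 8.2, 16.2 and 19.1 list hospitalization, ventilation and 30-day death as separate complications. Section 19.1 words the later items as "ii) respiratory failure requiring mechanical ventilation; (iii) death within 30 days and (iv) Time to a Ct value of non-detectable".
- **Test.** Section 19.2.2 takes hospitalization as item (i) and continues that "respiratory failure requiring mechanical ventilation; and (iii) death within 30 days will be compared using" Fisher's exact test. It adds: "All additional tests will be two-sided and tested at level alpha=0.05". It limits the hospitalization item to patients who were not inpatients at entry. Ventilation has no matching limit, although Section 3.4 excludes ventilated patients from the Expansion Cohort only above an FIO2 of 60%.
- **Benchmark.** Section 8.2 states that "approximately 40% are expected to have the composite endpoint of respiratory failure requiring mechanical ventilation or death". It does not split this rate into its components, and no analysis in Section 19 uses the composite.
- **Weight.** Section 8.2 opens its caveat with "Although the study is not powered for the clinical endpoint", but continues that if "any of the elements of the clinical efficacy endpoint will reach statistical difference between arms", that endpoint overrules as the measure of efficacy. Section 16.2 marks ventilation alone, within the secondary list, as the primary efficacy endpoint.
- **Death before the event.** No section says how a patient who dies without ventilation or hospitalization is coded on that element. Section 19.8, on missing data, does not address it.
- **Follow-up.** Section 7 follows patients to Day 30. Both calendars in Appendix F run survival follow-up through Day 14, and their footnotes refer to 14-day (Main) and 15-day (Expansion) survival. The Main Cohort calendar has no Day 30 visit.

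**The concern.** Death competes with ventilation. A patient who dies of respiratory failure without being intubated, for example after a decision not to intubate or after a rapid decline, can no longer have the ventilation event. With no rule, a yes/no count records a non-event. The same holds for hospitalization when a patient dies at home.

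Early death or less frequent intubation therefore lowers the ventilation frequency without any patient doing better. The trial is non-randomized, so intubation practice may differ between treated patients and whatever group they are compared with. This would matter little if ventilation were only a descriptive count. Here a significant ventilation result can by itself become the overruling evidence of efficacy, ahead of the viral-load endpoint, while the rate of ventilation or death is unchanged.

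**Working it through.** **Inputs from the plan.** Composite rate of ventilation or death: about 40% (Section 8.2). Two-sided alpha of 0.05 for each clinical test (Section 19.2.2). Treated patients: 10 in Phase IIa (Section 19.1) and up to 20 in the Expansion Cohort (Section 4.1).

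**Inputs assumed, because the plan gives none.** The share *f* of composite events that are deaths without ventilation, and the number of controls. The 40% is cited from outside, so there is no calculation behind it to reproduce. The plan's one sample-size calculation concerns the Ct AUC and does not bear on this point.

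**Step 1: what the count loses.** Ventilation frequency = 0.40 × (1 − *f*), with the composite held at 40%.

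| *f* | Ventilation frequency | Expected ventilated, n=10 | Expected ventilated, n=20 |
|---|---|---|---|
| 0 | 40% | 4 | 8 |
| 0.25 | 30% | 3 | 6 |
| 0.50 | 20% | 2 | 4 |
| 0.75 | 10% | 1 | 2 |

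This is arithmetic, not evidence about the trial. It shows why the 40% cannot be set against a ventilation-only frequency.

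**Step 2: one worked data set, 20 treated and 20 controls.** Treated: 0 ventilated, 8 dead without ventilation. Controls: 6 ventilated, 2 dead without ventilation. Two-sided Fisher tests:

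- Ventilation alone, 0/20 v 6/20: p=0.020, favouring treatment.
- Ventilation or death, 8/20 v 8/20: p=1.0.
- Death, if none of the 6 ventilated controls dies, 8/20 v 2/20: p=0.065, against treatment. If all 6 die, it is 8/20 v 8/20: p=1.0.

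So ventilation reaches significance, the plan's own death test does not, and no rule requires the elements to agree before one of them overrules.

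**Step 3: how often, over a range of shares.** Take 20 treated and 50 controls, with a true composite of 40% in both groups and *f* = 0.25 in controls (ventilation frequency 30%). Let X ~ Bin(20, 0.40 × (1 − *f*)) be the ventilated count in treated patients and Y ~ Bin(50, 0.30) the count in controls. Sum the joint probability over all pairs (X, Y) where X/20 < Y/50 and the two-sided Fisher p is at most 0.05.

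| Unventilated-death share, treated / control | Ventilation frequency, treated / control | Ventilation alone falsely favours treatment |
|---|---|---|
| 75% / 25% | 10% / 30% | 33% |
| 50% / 25% | 20% / 30% | 8.3% |
| 35% / 25% | 26% / 30% | 3.1% |
| 25% / 25% | 30% / 30% | 1.5% |

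The same calculation on the composite (40% v 40%, 20 v 50) gives 1.7% whatever the shares. With 10 treated and 50 controls, ventilation alone gives 15.5% at 75/25 and 5.0% at 50/25. The error comes from a difference in shares between the groups. When the shares are equal it disappears.

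**The case against.** **Deaths are not hidden.** Thirty-day death has its own test at the same alpha, and Section 19.1 promises contingency tables and individual listings. A careful reader of the results would see the unventilated deaths. This stands, and it rules out any inference that the plan conceals them. It does not repair the ventilation count. In the worked example the death test reaches p=0.065 at its strongest and weakens as ventilated controls die.

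**The plan does not say that such deaths are favourable.** A reader might infer a stated scoring rule. There is none. The non-event coding is only what a literal count yields when the plan is silent.

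**The 40% is not the plan's only benchmark.** Section 19.3 sets an institutional AUC benchmark of 130, which drives the primary test. The 40% is the only benchmark for clinical outcome.

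**The false-favour rates rest on assumptions.** The documents give no split of the composite and no clinical control group. The historical controls in Sections 2.6 and 19.1 are described for viral load, and Phase IIa is single-arm. This also stands: the 33% needs a threefold gap in shares that nothing in the documents supports.

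**The stakes are limited.** These are secondary endpoints, the plan says it is not powered for them, and Section 2.6 leaves clinical efficacy to a larger randomized trial. That argument would be enough without the overruling clause and the label in Section 16.2, which give a single element more weight than a secondary count should carry.

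**Conclusion.** The concern holds as a gap in endpoint definition that the overruling clause makes consequential. Ventilation is tested alone, is labelled primary for efficacy in one section, and may overrule, while death before ventilation has no rule and the composite that carries the 40% is never analysed. A ventilation result at p=0.020 can stand beside an unchanged composite at p=1.0.

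The frequency of this error is not known. Under the assumed 20 v 50 comparison with equal 40% composites it runs from 1.5% with equal shares to 33% at an extreme 75/25. A reader might take the 33% as this trial's error rate; the documents do not support that, because it depends wholly on an assumed difference in unventilated deaths. This is a change that the sponsor should make because it is cheap. It is not a flaw in the primary viral-load analysis.

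**What to change.** 1. **Sections 19.1 and 19.2.2:** make mechanical ventilation or death within 30 days the tested clinical endpoint, matching the 40% in Section 8.2. Count the ventilation component as new ventilation in patients not ventilated at entry.
2. **Same sections:** in patients who were not inpatients at entry, count death as an event in the hospitalization endpoint.
3. **Ventilation alone:** report it descriptively, with deaths without ventilation beside it.
4. **Section 8.2:** limit the overruling clause to the composite.
5. **Section 16.2:** remove the primary-efficacy label from ventilation alone.
6. **Appendix F:** reconcile the Day 14 and Day 15 survival wording with the 30-day death endpoint and the Day 30 follow-up in Section 7.

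**Cost.** Mostly wording. Ventilation alone loses its stand-alone test. Vital status at Day 30, and new ventilation up to then, must be recorded for every patient; Section 7 already plans follow-up to Day 30, but the Main Cohort calendar needs an entry for it. These changes do not settle who the Fisher comparison group is. That has to be defined separately.
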